18.0 INCLUSION /EXCLUSION CRITERIA

18.1 INCLUSIONS

1. Age \geq 18 years of age
2. Prescription pharmacologic treatment is insufficient for treatment of pain
3. Pain duration of \geq 6 months
4. Pain limits physical activity

5. Pain occurs daily
6. Chronic low back pain, with or without leg pain, associated with MRI or other imaging study consistent with lumbo-sacral spine disease with or without nerve compression
7. Failed back surgery patients without metal implant
8. Pain intensity ≥ 5 at the time of enrollment and a self-reported pain score of ≥ 4 over the 7 preceding days.

18.2 EXCLUSIONS

1. Life expectancy ≤ 6 months
2. Oral opiate doses or active ingredient has changed significantly in past 12 months*
3. Received intraspinal medication (e.g., epidural, intrathecal) in the lumbar region of the back within the past 3months
4. Use of intravenous pain medication in the past 3months**
5. Active use of transcutaneous electrical nerve stimulator (TENS) (within 30 days)
6. History of seizures
7. History of implanted medical device, cardiac pacemaker, implantable cardiac defibrillator, or other implant above the knee (Cochlear etc)
8. History of cardiac dysrhythmias
9. Member of a vulnerable population
10. Current or potential legal action of disability claim related to back pain
11. Body Mass Index (BMI) of > 40
12. Another pain condition that might confound results (e.g. back pain above the waistline)
13. Pregnant women
14. Inability to undergo study assessments or complete questionnaires independently
15. Metal objects in the body above knee(i.e. Aneurysm clip, bullet fragment)
16. Active psychological co-morbidities (i.e. uncontrolled schizophrenia)

19.0 VISITS/PHONE ASSESSMENTS

Screening process ~ 60 minutes

Eligibility confirmation (baseline), informed consent, randomization and treatment (if enrolled) visit ~ 90 minutes

48-hour reminder follow-up telephone call ~30 minutes

Final 7& 30 day assessment telephone call ~ 30 minutes

The date of treatment will be used to calculate the time for follow-up visits.

20.0 Group Allocation

Block randomization to treatment group 1 (n = 10) or 2 (n = 10). We will use the RAND function in Excel to assign a random number from 1-20 to each of our participants. Participants who are randomly assigned odd numbers will be assigned to the intervention group. Participants who are randomly assigned even numbers will be assigned to the control group.

20.0 SCHEDULE OF EVENTS (SEE TABLE BELOW)

Informed consent

7-day pain diary to confirm eligibility (Self-report)

Enrolled or deemed ineligible

Randomization

Randomized treatment

1-, 2-, 4-, 6-, 8, 12, 24, and 48-hour follow-up

24-hour follow-up (± 8 hours)

48-hour follow-up (± 8 hours)

72-hour follow-up (± 8 hours)

Final assessment 7 & 30 day follow-up telephone call (+ 3 days)

21.0 STUDY DURATION FOR SUBJECT

Duration of the study for a subject, including follow-up, will be approximately 30 days

22.0 DURATION OF STUDY

Recruitment, treatment, follow-up and data analysis will require approximately 120 days.

23.0 SUBJECT DISCONTINUATION OR STUDY SUSPENSION

Eligible, randomized subjects will be replaced if lost

Study enrollment will be suspended pending principal investigator's decision in response to any SAE

Individual participation will be suspended pending physician disposition in the presence of any SAE

We will request that withdrawn subjects continue to fill out the study questionnaires and allow us to collect data.

24.0 PROTOCOL DEVIATIONS

Protocol deviations will be recorded.

25.0 DATA COLLECTION/CASE REPORT FORMS

Researchers not involved in patient clinical care will collect data. During all study phases, all data will be collected on paper CRFs and later entered into the eCRFs for storage in the secured password-protected database. This study will utilize REDCap for data collection, transmission and storage. REDCap (Research Electronic Data Capture) is a secure, web-based application for building and managing online databases. All study data will be entered via a password protected, study unique REDCap database website. REDCap servers are housed in a data center at Vanderbilt University and all web-based information transmission is encrypted. REDCap was developed specifically around HIPAA-Security guidelines. REDCap has been disseminated for use at many institutions and currently supports > 140 academic/non-profit consortium partners and 11,000 research end-users (www.project-redcap.org).

26.0 DATA ANALYSIS

Descriptive statistics, trend analysis of endpoint means for effectiveness. Tabular collection of adverse events with narrative

STUDY SCHEDULE AND DESCRIPTION OF DATA COLLECTION

Time of data collection	Data collected						
	Log entry	Demographics	History	Informed consent	NPRS first rating or since last rating given	AE	Additional endpoints
*Eligibility screened and offered participation	X	X	X	X			
*Pain each day in 7-day period					X	X	
Day 1 (baseline = start of treatment)					X	X	X
During treatment: 5 minutes					X	X	
10 minutes					X	X	
After treatment: 1 hour					X	X	
2 hours					X	X	
3 hours					X	X	
4 hours					X	X	
8 hours					X	X	
12 hours					X	X	
24 hours					X	X	
48 hours					X	X	
72 hours					X	X	
*Final assessment 7 & 30 days (+3)		X (employment status only)			X	X	X

*Data can be collected in person, via mail, via telephone, email, or fax

LAY SUMMARY

The study will evaluate whether an experimental medical device that emits a brief, intense magnetic field will relieve pain in the low back. The United States Food and Drug Administration (FDA) has approved a similar device for treatment of migraine, but this type of device has not been studied for the treatment of low back pain. No significant adverse reactions or side effects have been reported from the use of magnetic stimulation for headache treatment. Some patients who have migraine headaches have excellent pain relief with the magnetic treatment even if they did not get pain relief with medications.

We do not know whether magnetic treatment will relieve low back pain, so we will test this by applying a powerful electromagnet to the painful area of the low back. In some subjects, the magnet will be turned on, but in other patients the magnet will not be turned on. Neither subjects nor subjects' treating doctor will know whether the magnet was turned on or not, although the study team will know which subjects received treatment with magnetic pulses. The effect on pain will be recorded periodically for 2 days. If the subjects' reported pain is reduced as a result of the magnetic treatment compared with subjects who did not have the magnet turned on, then the magnet might have reduced the pain. Additional studies will be needed to further investigate whether this therapy reduces low back pain.

Keywords: **low back pain, TCMS (Transcutaneous Magnetic Stimulation), TENS (Transcutaneous Electrical Nerve Stimulation)**

RATIONALE AND BACKGROUND

Approximately one third of the population suffers from acute and chronic pain at any given time, and the lifetime incidence of low back pain is 80%. Pain has been called a silent epidemic. Treatment of pain with medication incurs significant risks and side effects; even over-the-counter medication causes occasional fatalities (e.g., acetaminophen or Tylenol can cause liver toxicity; and nonsteroidal anti-inflammatory drugs, such as aspirin and ibuprofen, can cause bleeding). Opioid medications have a significant potential for abuse, addiction, and adverse reactions, such as respiratory depression and death.

Electrical stimulation for the relief of pain has been used since antiquity, and with the development of compact power sources and solid state electronics in the last century, it has become commonplace. Electrical stimulation has been applied to the peripheral (e.g., in the limbs) as well as the central (brain and spinal cord) nervous system, using implanted as well as external noninvasive devices.

Electrical stimulation specifically for low back pain, the condition addressed in this protocol, is supported by high quality clinical trial evidence for spinal cord stimulation (SCS), using surgically implanted electrodes and pulse generators. Randomized controlled trials have shown that SCS is superior to optimal medical management and to repeated low back surgery in patients with persistent or recurrent low back and leg

pain following spinal surgery (North et al., 2005). High frequency SCS has been effective for low back pain in particular. SCS has been in use for nearly 50 years. Medtronic, Inc.; St. Jude Medical, Inc.; and Boston Scientific Corporation all have FDA-approved devices, which require surgical implantation and maintenance for the production of electrical pulses to relieve pain.

Subcutaneous peripheral nerve field stimulation targets low back pain via electrodes implanted directly over the painful area and is less invasive than SCS even though it uses the same implanted pulse generators as SCS (Barolat et al., 2009).

Transcutaneous electrical nerve stimulation (TENS), a noninvasive technique, has been used for several decades to treat low back pain. TENS passes current through intact skin via surface electrodes with conductive gels and adhesives. TENS is available without a prescription but is not free from side effects, notably skin pain caused by recruitment of small nerve fibers immediately beneath the surface of the skin [Barker 85], which limits the usage amplitude of the electrical current and thus makes it difficult to stimulate deep structures.

Compared with electrical stimulation, magnetic stimulation has a much shorter history [Thomson 1910]. Magnetic stimulation is an application of Faraday's Law, whereby a high intensity magnetic pulse generates an electrical pulse within conductive media, including excitable tissue, viz., nerve and muscle. Magnetic stimulation has been used to stimulate peripheral nerves selectively [Oberg 73, Polson 82]. Compared with other forms of stimulation, transcutaneous magnetic stimulation (TCMS), which is administered through intact skin, can create larger electrical currents in nerves at greater depth with little, if any, skin pain [Barker 85]. In fact, magnetic stimulation can act through the skin and the skull to stimulate the brain, minimizing recruitment of overlying structures, such as pain fibers in the scalp. Such transcranial magnetic stimulation has been used extensively for the diagnosis and treatment of neurological disease (e.g., stroke) and treatment of psychiatric disease (e.g., depression). Repetitive transcranial magnetic stimulation [Wassermann 98] has been used to treat a number of pain conditions. A meta-analysis of repetitive transcranial magnetic stimulation, demonstrates effectiveness for craniofacial pain syndromes [Leung 09]. "Single pulse" transcranial magnetic stimulation (at a much lower power than used in repetitive TMS) has been effective for migraine using a device that can deliver pulses, each of duration less than 1 msec, as often as every 30 seconds [Lipton 10, Diener 10].

TCMS (of the periphery), unlike transcranial magnetic stimulation, has received little attention as a treatment for pain; it has been the subject of a single published case series, with reportedly positive results in 5 patients with painful peripheral nerve injury or neuroma [Leung 14]. Modification of peripheral nerve activity—even if it is distal or collateral—in the same segment as a pain generator can afford substantial relief (North et al., 1996). The development of an effective, minimal risk, non-invasive treatment of pain without medication would represent a significant advance in the field.

The first commercial magnetic TCMS stimulators were produced in Sheffield in 1985. These devices consist of a capacitor charge/discharge system with associated control and safety electronics. Using the charging circuitry, the capacitor stores energy to a preset level. When the device receives a trigger input signal, the stored energy, apart from that lost in the wiring and capacitor, is transferred to the stimulating coil and then returned to the instrument to reduce coil heating.

The most widely used description of the output of magnetic stimulators is “magnetic field strength,” although this refers to the density of magnetic flux rather than total magnetic flux and is a poor measure of output produced by the stimulating coil over its total area. In a small coil, where the magnetic flux is concentrated in a small area, the magnetic field intensity is higher than in a larger coil, but the field falls off much more rapidly with distance. Hence a small coil is somewhat more powerful in the stimulation of superficial nerves, and a large coil is more suitable for structures at depth. The amplitude, waveform, and spatial characteristics of the induced current all play a role in magnetic nerve stimulation.

A more accurate indicator of the stimulating power output is the induced charge density per phase defined as the integral of the induced current density during the rise time of the magnetic field. Unlike magnetic field strength, induced current density takes into account the effects of the amplitude and the duration of the induced stimulating current. Induced current density does not, however, consider the effects of the nodal time constant of the myelinated nerve fiber. Unfortunately, the actual value of the induced charge density per phase is difficult to calculate accurately due to the complexities of the structure being stimulated. Different areas, such as bone, fat, grey matter, and white matter, with differing conductivities all affect the induced current and its path.

The stimulating coil is the only part of a magnetic nerve stimulator that needs to come close to, or into contact with, the patient. During the discharge of the magnetic pulse, the coil winding is subjected to high voltages and currents. Although the pulse generally lasts for less than 1ms, the forces acting on the coil winding are substantial and depend on the coil size, peak energy, and construction. Careful coil design is, therefore, a very important aspect in the construction of a magnetic stimulator. Compared with a small coil, large coils contain more copper mass and generally have a lower electrical resistance; as a result, less heat is dissipated in the windings of large coils, and because of their higher heat capacity, they remain usable for much longer periods before becoming warm.

Since the magnetic field strength falls off with distance from the stimulating coil, the stimulus strength is at its highest close to the coil surface. The stimulation characteristics of the magnetic pulse, such as depth of penetration, strength, and accuracy, depend on the rise time, the peak magnetic energy transferred to the coil, and the spatial distribution of the field. The rise time and the peak coil energy are governed by the electrical characteristics of the magnetic stimulator and stimulating coil,

whereas the spatial distribution of the induced electric field depends on the coil geometry and the anatomy of the region of induced current flow.

Reference

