7.0 DESIGN

Single-site, randomized, single -blind, placebo-controlled, trial

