8.0 INTERVENTION

Subjects will identify the location of pain on their back. A member of the study team will note the location on a drawing. The TCMS device will be placed at the site the patient

identified. (Low back pain is defined as pain below the costal margin posteriorly, extending as low as the upper buttocks.)

With only a hospital gown intervening, the clinician will place the active or sham TCMS device on the area of pain, turn the device on, and adjust the amplitude upward from 0.24T in increments of 10%, approximately every 6-10 seconds, until the 1.2T setting is achieved or the subject reports discomfort. If the patient reports discomfort, the amplitude will be adjusted downward as necessary to maintain patient comfort.

Treatment group: TCMS device set to 1.2 Tesla will deliver a dose of 10 pulses per minute for 9 minutes (total 90 pulses). The first minute will be dedicated to adjusting the amplitude until maximum is achieved and/or the subject reports a sensation.

Placebo group: the sham TCMS device will remain on the area of pain for 10 minutes. The sham TCMS device is engineered so as to make the same sound at the same intervals as the active device. The same procedures will occur as those with the active device. The first minute will be dedicated to adjusting the “sham” amplitude. The remaining 9 minutes will be the treatment period.

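### Data collectors are separated from clinical care but not masked, so ratings, calls and adverse-effect records may be taken by people who know the arm

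*Combined protocol and SAP*

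**What the plan says.** Section 7.0 declares the design: "Single-site, randomized, single -blind, placebo-controlled, trial". The Lay Summary, which follows Section 26.0, says who is blind. Neither the subject nor the subject's "treating doctor will know whether the magnet was turned on or not", whereas "the study team will know which subjects received treatment with magnetic pulses". It does not define the study team.

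Section 25.0 says of data collection: "Researchers not involved in patient clinical care will collect data". It does not say whether these researchers belong to the study team or whether they may see the allocation.

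Section 20.0 (Group Allocation) relies on a spreadsheet function to "assign a random number from 1-20 to each of our participants". The arm then depends only on whether that number is odd or even. The rule for the active arm is that "Participants who are randomly assigned odd numbers will be assigned to the intervention group", and the matching rule for the other arm is that "Participants who are randomly assigned even numbers will be assigned to the control group". The documents do not say who holds the list, or whether the number appears on a CRF or serves as a study ID.

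In Section 8.0, "the clinician will place the active or sham TCMS device on the area of pain" and adjusts the amplitude. The same section describes a sham matched in sound and timing, which protects the subject's blinding.

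**The concern.** Being outside clinical care is not the same as being unaware of the arm. Read literally, the plan allows a collector who knows the allocation to take pain scores, hold the follow-up calls and write down unwanted effects. The main outcome is a subjective 0-10 score. Prompting, tone or persistence that differs by arm can change what is recorded even when the subject is blind.

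Three results are exposed: the active-versus-sham comparison of change in NPRS (Section 12.0), the responder part of study success (Section 11.0) and the adverse-effect tables (Section 14.0). With 10 subjects per arm, one or two changed classifications matter. The 3-of-10 rule counts the active arm only, so the sham arm cannot offset a shift confined to active subjects.

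**Working it through.** **1. Is anyone who collects data masked?** The four places that bear on this are:

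| Place | What it settles | What it leaves open |
|---|---|---|
| Section 7.0 | One level of blinding | Who is blind |
| Lay Summary | Subject and treating doctor blind; study team not | Who is in the study team |
| Section 25.0 | Collectors are outside clinical care | Whether they know the arm |
| Section 20.0 (Group Allocation) | Odd means active, even means control | Who sees the number |

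No section masks the collectors or callers. The numbers 1-20 contain 10 odd and 10 even values, so with each used once the number identifies the arm of all 20 subjects to anyone who sees it. If collectors are study team, the Lay Summary already gives them the arm. If they are not, the number is a possible second route.

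**2. Where is staff contact documented?** Inside the 48-hour success window the listed contacts are the treatment visit (5- and 10-minute scores) and the reminder call at 48 hours (Section 19.0). The schedule's footnote on how data may be collected is starred for screening, the diary and the 7- and 30-day assessment only. How the 1- to 24-hour ratings are obtained is not stated. The 7- and 30-day calls fall after the window and cannot change treatment success.

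**3. How sensitive is the 3-of-10 rule?** The plan gives no alpha, power, effect size or SD, so there is no figure of its own to reproduce. For an assumed recorded response rate p,

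P(X ≥ 3) = 1 − [(1−p)^10 + 10p(1−p)^9 + 45p²(1−p)^8].

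- p = 0.10: 0.070
- p = 0.20: 1 − (0.107 + 0.268 + 0.302) = 0.32
- p = 0.30: 1 − (0.028 + 0.121 + 0.233) = 0.62

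A 10-point rise in recorded response from 20% to 30% would nearly double the chance of meeting the responder criterion.

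**4. What might a recording shift do?** At an assumed baseline of 6, a 30% reduction is 0.30 × 6 = 1.8 points, so a half-point shift supplies 0.5/1.8 = 28% of it.

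The simulation has no device effect. Its assumptions are person mean 6, between-person SD 1.3, within-person SD 1.5, and autocorrelation time 6 or 24 hours (which gives each range). The eligibility limits applied are a diary mean of at least 4 and a Day 1 score of at least 5. Ratings are at the Section 9.3 and 9.4 times, and the simulated response rate goes into the formula above.

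| Ratings shifted; persistence rule | No shift | 0.5 point | 1 point |
|---|---|---|---|
| All; two consecutive ratings | 8-11% | 33-42% | 70-81% |
| 5 min, 10 min, 48 h; relief spans about 1 hour | 8-12% | 10-15% | 12-19% |
| As above plus the 1-hour rating | 8-12% | 15-20% | 32-37% |
| 5 min, 10 min, 48 h; any two consecutive ratings | see note | 18-23% | 37-44% |

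Entries are the chance of at least 3 of 10 responders. In the first row the response rates are 11-12%, 20-23% and 34-38%. The last row starts slightly above the others because 5 and 10 minutes alone can qualify. That reading is looser than the 1-hour persistence in Section 11.0. Coding choices, such as rounding to whole scores, move the entries by several points.

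**The case against.** The best defence is that single-blind was chosen and disclosed. The subjects who produce the scores are blind and have a sound-matched sham, and the trial is preliminary and expressly unpowered. This stands as far as it goes: nothing is hidden, and subject blinding limits the bias. It does not remove it, and a single-blind design does not require collectors who know the arm.

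A reader might infer more than the documents support:

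- **That the blinding statements contradict each other.** They do not. Single-blind is compatible with a study team that knows the allocation.
- **That odd and even numbers disclose the arm to collectors.** This happens only if they see the number, and no section says they do.
- **That the device operator in Section 8.0 is the blinded treating doctor.** They may be different people. This needs clarifying but is not a demonstrated conflict.
- **That collectors judge whether a serious adverse event is related.** No section assigns that judgement to them. Section 23.0 refers decisions after such events to the principal investigator and the physician.
- **That 33-42% or 70-81% is the expected effect.** Those figures need staff influence on every rating, which the documents do not describe.
- **That masking is free, or that every recorder can be kept out of the treatment room.** Scores and adverse events are recorded at 5 and 10 minutes, during treatment, and staffing is not given.

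**Conclusion.** The gap is real. The plan discloses allocation to an undefined study team and leaves the separate collectors unmasked, so outcome and adverse-effect data may be gathered with knowledge of the arm. It is an avoidable design weakness and should be closed before data collection, because analysis cannot repair it afterwards.

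Its size is uncertain. Any shift in recording is an assumption, and so is the set of ratings it reaches. For a half-point shift, the chance of at least 3 of 10 responders without a device effect becomes 10-15% if only the documented contacts are affected and relief must last about an hour. It becomes 33-42% if every rating is affected, which is the upper end as regards staff contact. The adverse-effect records and the 7- and 30-day outcomes are exposed as well, though no figure can be put on that. Masking would remove influence from knowing the arm. It would not remove the 8-12% chance of meeting the responder criterion with no shift at all.

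**What to change.** - **Section 25.0:** state that the researchers who take post-treatment ratings, make the 48-hour, 7-day and 30-day calls, and record adverse effects after the treatment session have no access to the allocation list or the random number.
- **Section 20.0 (Group Allocation):** limit knowledge of the allocation to the device operator and a named role that holds the list. Keep the odd/even number off the CRFs and use study IDs unrelated to it.
- **Sections 9.3 and 15.0:** have subjects write their own 5- and 10-minute scores, with the operator recording events during treatment.
- **Section 9.4:** say how the 1- to 24-hour ratings are obtained.
- **Lay Summary and Section 8.0:** say exactly who knows the allocation, and whether the clinician applying the device can be the treating doctor described as blind.

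The cost is wording plus ID and list handling. Separate collectors and a sound-matched sham are already planned. Whether extra staff time is needed cannot be judged from the documents. One limitation remains: events during treatment are still recorded by an operator who knows the arm, and the report should say so.
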